I understand that the Sponsor may decide to suspend or prematurely terminate the study at any time for whatever reason; such a decision will be communicated to me in writing. Conversely, should I decide to withdraw from execution of the study, I will communicate my intention immediately in writing to the Sponsor.

Print Name	Signature
Title	Date (DD MMM YYYY)

SUMMARY OF CHANGES

Please refer to the comparison document for Protocol Version 3.0 (dated 16 Jan 2023) versus Protocol Version 2.0 (dated 03 Oct 2022) for actual changes in text. The Summary of Changes below is a top-line summary of major changes in the current DS1211-A-U201 clinical study protocol (Version 3.0) by section.

[figure not shown]
Amendment Rationale:

CONVENTIONS USED IN THIS SUMMARY OF CHANGES

All locations (section numbers and/or paragraph/bullet numbers) refer to the current protocol version, which incorporates the items specified in this Summary of Changes document.

Minor edits, such as update to language that does not alter original meaning, update to version numbering, formatting, change in font color, corrections to typographical errors, use of abbreviations, moving verbiage within a section or table, change in style, or change in case, are not noted in the table below.

CONVENTIONS USED IN THIS SUMMARY OF CHANGES				
CCI				

PROTOCOL SYNOPSIS

Protocol Title

A Phase 2, 12-Week, Randomized, Double-Blind, Placebo-Controlled Study of DS-1211b in Individuals with Pseudoxanthoma Elasticum

Protocol Number

DS1211-A-U201

Sponsor/Collaborators

Daiichi Sankyo, Inc.

Registry Identification(s)

TBD: NCT Number: ###, EudraCT Number: 2022-000676-19, or RCT Number: ### as applicable]

IND Number

IND Number 135092

Study Phase

Phase 2

Study Design

Study DS1211-A-U201 is a 12-week, randomized, double-blind, placebo-controlled, parallel-group study that aims to assess the safety, tolerability, and pharmacokinetic (PK) and pharmacodynamic (PD) dose response of DS 1211b in individuals with pseudoxanthoma elasticum (PXE) by using biomarkers relating to tissue-nonspecific alkaline phosphatase (TNAP) inhibition.

of DS 1211b or placebo in tablet form for once daily dosing for a total of 12-week dosing, followed by a postdose biomarker assessment and a 2-week follow-up safety check. Approximately 12 to 16 individuals with PXE will be enrolled in each group.

Study Completion

The study completion date will occur when all study participants have completed their follow-up safety check or discontinued from the study early.

Planned Geographical Coverage, Study Sites and Location

The study will be conducted at approximately 10 study sites located in the US and possibly in the European region.

Study Population

Adult individuals with an established diagnosis of PXE

Study Objectives/Outcome Measures and Endpoints

The table below lists primary study objectives and endpoints with outcome measures.

Objectives Outcome Measure		Endpoints	Category					
Primary	Primary							
To assess the safety and tolerability of DS-1211b compared with placebo in subjects with PXE	Title: Safety parameters Description: Descriptive statistics of safety endpoints Time frame: From the time the subject signs the study informed consent form (ICF) and up to Day 98 (14 days after the last dose of study drugs)	Incidence of adverse events (AEs), including serious adverse events (SAEs), and treatment-emergent AEs, physical examination/assessment findings including vital sign measurements, standard clinical laboratory parameters, and electrocardiograms	Safety					
To assess the dose response by assessing the treatment changes in PD endpoints	Title: PD endpoints Description: Profiles of alkaline phosphatase (ALP) and TNAP substrates Time frame: Data are collected at baseline through Day 98.	ALP, inorganic pyrophosphate (PPi), and pyridoxal 5'-phosphate (PLP)	Pharmacodynamic					
Secondary								
To characterize the PK of DS- 1211a (the free form of DS-1211b in plasma) in subjects with PXE Title: PK endpoints Description: Plasma concentration and PK parameters of DS-1211a Time frame: Data are collected at baseline through Day 84.		Plasma concentration and PK parameters of DS-1211a Include, but are not limited to, maximum plasma concentration, time to reach maximum plasma concentration, trough plasma concentration, trough plasma concentration-time curve during dosing interval, area under the plasma concentration-time curve up to the last quantifiable time, and area under the plasma concentration-time curve up to infinity (if possible to calculate)	Pharmacokinetic					

Study Duration

The study start date is the date when the first prospective study participant has signed the ICF. A PXE individual will be considered as eligible for randomization when the Investigator or designee has obtained written consent and confirmed all eligibility criteria have been met during the screening period and when all screening procedures have been completed.

Anticipated total duration of the study is expected to be approximately 5 months for individual study participants.

Study Population/Eligibility Criteria

Study participants must satisfy all of the following criteria to be included in the study:

- Sign and date the ICF, prior to the start of any study-specific qualification procedures.
- Are male or female participants aged 18 to 75 years at screening.
- Have an established diagnosis of PXE, with typical ocular and dermatological clinical features^{1,2}:
 - Ocular findings angioid streaks or peau d'orange
 - Skin findings characteristic PXE papules and plaques or diagnostic histopathological changes in lesional skin
- Are fully vaccinated for coronavirus disease 2019 (COVID-19) per current CDC guidelines.
- For women of childbearing potential (not postmenopausal as a result of either natural or
 postsurgery cessation of menses), must have a negative serum pregnancy test at screening
 and must be willing to use an effective method of birth control, as detailed in Section 17.2
 upon entering study screening, during the treatment period, and up until the time of the
 follow-up visit.
- Is willing and able to comply with scheduled visits, drug administration plan, laboratory tests, other study procedures, and study restrictions.

Individuals who meet any of the following criteria at screening will be disqualified from entering the study:

- Have a history of bone fracture in the past 6 months.
- Have a history of active metabolic bone disease that significantly affect the interpretation
 of study biomarker results, excluding osteopenia or osteoporosis without fragility
 fracture.
- Have a history of calcium pyrophosphate deposit disease such as chondrocalcinosis, pseudogout, pyrophosphate arthropathy.
- Have a history of hypophosphatasia.
- Have a history of untreated hyperparathyroidism.
- Participated in another interventional research study in the past 60 days.
- Are participating or participated within the last 12 months in PXE trials (eg, trials with PPi, PPi analogues such as bisphosphonate, or ENPP1 and its analogues) or in clinical trials relating to bone mineralization.
- Used bisphosphonate in the preceding 12 months or had plans to use bisphosphonate during the study.
- Used strong inhibitors or inducers of Cytochrome P450 isozymes, 2C19, 3A4, or 3A5.
- . 50
- Have an alkaline phosphatase < lower limit of normal (LLN) range.
- Have alanine aminotransferase or aspartate aminotransferase >2 × upper limit of normal (ULN) range; total bilirubin > 1× ULN.
- Have PLP > ULN.
- Have hemoglobin <10.0 g/dL.

- Have a QTcF interval duration >450 ms at screening.
- Have moderate to severe renal insufficiency (Creatinine clearance <60 mL/min by Cockcroft-Gault method).
- Are pregnant or breast-feeding women.
- Were women of childbearing potential unwilling to use contraceptive methods.
- Have a history of sulfonamide allergy.
- Have any elective surgery planned during the study period.
- Have any other significant condition (medical, psychiatric, social, or medication) that, in the judgment of the Investigator, would prevent full participation or would be inappropriate for the study.

Investigational Medicinal Product, Dose, and Mode of Administration

- Matching placebo tablets
- Tablets to be administered orally for once daily dosing.

Planned Sample Size and Key Statistical Analysis

CCI

Sample size is not

based on statistical consideration but is chosen on the basis of feasibility and clinical consideration from biomarker results of the completed Phase 1 healthy volunteer studies.

Safety endpoints, difference in biomarkers between active doses and placebo, plasma concentration of DS-1211a, and PK parameters will be summarized by descriptive statistics. Plasma concentration of DS-1211a will be also analyzed by noncompartmental methods. Observed values at each assessment and the absolute change and percentage change from baseline will be numerically summarized for primary and exploratory biomarkers by treatment group over time. The 95% confidence interval will be presented for percentage change from baseline in PPi and PLP.

TABLE OF CONTENTS

INVES	TIGATOR AGREEMENT	2
SUMM	ARY OF CHANGES	3
PROTO	OCOL SYNOPSIS	5
LIST O	F ABBREVIATIONS	15
1.	INTRODUCTION	17
1.1.	Background	17
1.2.	Study Rationale	17
2.	OBJECTIVES, OUTCOME MEASURES, AND ENDPOINTS	18
2.1.	Study Objectives	18
3.	STUDY DESIGN	20

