2.1. Study Objectives

The objectives, definitions of associated endpoints as well as applicable outcome measures are described in Table 2.1. Further requirements for the endpoint analyses and censoring rules, where applicable, can be found in Section 11.4 Section 11.5, and Section 11.6.

Study results, based on the analysis of below endpoints, will be analyzed to assess the dose for future clinical trials.

Table 2.1: Description of Objectives, Outcome Measures, and Endpoints

Objectives	Outcome Measure	Endpoints	Category				
Primary							
To assess the safety and tolerability of DS-1211b compared with placebo in subjects with PXE	Title: Safety parameters during the study Description: Descriptive statistics of safety endpoints Time frame: From the time the subject signs the study ICF and up to Day 98 (14 days after the last dose of study drugs)	Incidence of AEs, including SAEs, and treatment-emergent AEs, physical examination/assessment findings including vital sign measurements, standard clinical laboratory parameters, and ECGs	Safety				
To assess the dose response by assessing the treatment changes in PD endpoints	Title: PD endpoints Description: Profiles of ALP and TNAP substrates Time frame: Data are collected at baseline through Day 98.	ALP, PPi, and PLP	Pharmacodynamic				
Secondary							
To characterize the PK of DS-1211a (the free form of DS-1211b in plasma) in subjects with PXE Title: PK endpoints Description: Plasma concentration and PK parameters of DS-1211a Time frame: Data are collected at baseline through Day 84.		Plasma concentration and PK parameters of DS-1211a Include, but are not limited to, Cmax, Tmax, Ctrough, AUCtau, AUClast, and AUCinf (if possible to calculate)	Pharmacokinetic				

[figure not shown]

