Coagulation	Х	X	X	Х	х		X	PT, aPTT and INR; predose (V2 to V5). Blood collection should follow ECG and vital signs if indicated at the same timepoint.
Chemistry	Х	X	X	Х	Х	Xe	X	Fasting required at all visits ^e except the postdose visit (Visit 6). Blood collection should follow ECG and vital signs if indicated at same timepoint. See Section 9.8 for details
Urine analysis	X	X			X			Fasted, use spot urine

Period	Screening	Baseline	Tre	atment	Period	Postdose	Follow-up	Notes
Visit Number	1	2	3	4	5 (EOT)	6	7	
Study Day	- 30 to -1	1	15	43	84ª	Last dose+3 ^{b,c}	98°	^a Or day of early discontinuation. ^b To be scheduled at 2 to 4 days after last dose (eg, Visit 5 or early discontinuation). ^c In-home visit unless otherwise specified by Investigator.
Window (days)			±3	±3	±3	±1	±5	
Pregnancy test	х	X	х	Х	Х		Х	Serum pregnancy tests to be performed at V1 Screening Visit. Urine pregnancy test to be performed at V2, V3, V4, V5, and V7. If positive, a serum pregnancy test should be performed.
Pharmacokinetic Assessments								
PK Sampling		X ^f	Xg	Xg	X^{f}			fFull collection/ § Sparse collection (See Table 3.2) Central laboratory testing. Blood collection should follow ECG and vital signs if indicated at same timepoint. Sampling will be obtained under nonfasted condition except for the predose samples, which will be collected after an overnight fast (≥ 8 hours). The windows for blood sample collection are as follows: 120 minutes at the predose timepoint and by ±10% of the nominal sampling time thereafter.
Pharmacodynamic Assessments								
ALP, PPi, and PLP	Xh	X ^f	Xg	Xg	X ^f	$\mathbf{X}^{\mathtt{h,i}}$	$X^{\mathrm{h,i}}$	fFull collection/g Sparse collection (See Table 3.2) h Single timepoint sample collection i ALP and PLP only Central laboratory testing. Blood collection should follow ECG and vital signs if indicated at same timepoint. All samples will be obtained under nonfasted condition except for the predose samples (Visits 2 to 5), which will be collected after an overnight fast (≥8 hours). The windows for blood sample collection are as follows: 120 minutes at the predose timepoint and by ±10% of the nominal sampling time thereafter.

Period	Screening	Baseline	Treatment Period			Postdose	Follow-up	Notes
Visit Number	1	2	3	4	5 (EOT)	6	7	

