11. STATISTICAL METHODS

11.1. General Statistical Considerations

Continuous variables will be summarized by the number of subjects, mean, standard deviation, median, and minimum and maximum values, unless otherwise specified. Categorical variables will be summarized by using frequency counts and percentages. In general, data will be summarized by treatment group.

Raw data will be presented with the exact precision with which they were collected.

There is no multiplicity adjustment.

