11.5.3. Biomarker Analyses

All biomarker analyses will be based on Biomarker Analysis Set. Observed values at each assessment and the absolute change and percentage change from baseline will be numerically summarized for primary and exploratory biomarkers by treatment group over time. The 95% confidence interval will be presented for percentage change from baseline in ALP, PPi, and PLP. The baseline of biomarker data is defined as the last nonmissing assessment collected prior to the first dose of study medication.

Difference in primary and exploratory biomarkers between active doses and placebo will be summarized by descriptive statistics.

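### The primary dose-response analysis of ALP, PPi and PLP, as written, names no main estimate per dose, no interval for dose versus placebo, and no analysis combining the three fasted on-treatment predose samples

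*Combined protocol and SAP*

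**What the plan says.** Section 2.1 lists as a primary objective "To assess the dose response by assessing the treatment changes in PD endpoints", with ALP, PPi and PLP as the endpoints, and gives the use of the results: "Study results, based on the analysis of below endpoints, will be analyzed to assess the dose for future clinical trials".

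The synopsis and Section 11.5.3 share the same core analysis sentence: "Observed values at each assessment and the absolute change and percentage change from baseline will be numerically summarized", by treatment group over time. Section 11.5.3 adds "The 95% confidence interval will be presented for percentage change from baseline in ALP, PPi, and PLP" and, for the comparison with placebo, "Difference in primary and exploratory biomarkers between active doses and placebo will be summarized by descriptive statistics". Section 11.1 states "There is no multiplicity adjustment".

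Table 3.1 schedules all three markers at Visits 2 to 5 (Days 1, 15, 43 and 84). Its note says that samples are nonfasted "except for the predose samples (Visits 2 to 5), which will be collected after an overnight fast". There are therefore three on-treatment predose samples taken under the same fasting condition as the Day 1 predose sample.

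Two passages point to further analysis without describing it. Section 3.2 mentions modeling and simulation at the end of the study, and Section 11.10 leaves biomarker methods and missing-data handling to a SAP.

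**The concern.** Three visits and three markers give nine predose pictures of dose response, and the text has no rule for which one counts if they rank the doses differently. The quantity that speaks most directly to the objective is the difference between a dose and placebo. As written it receives descriptive statistics only, while the 95% interval is attached to percentage change from baseline.

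The fasted predose samples at Visits 3 to 5 are comparable with one another and with baseline, yet no stated analysis uses them together. In arms this small, a combined estimate could be more precise at no cost in data. Section 3.2 says that dose choice turns on balancing the rise in PPi against the rise in PLP, so both the precision of each contrast and a clear main estimate matter.

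**Working it through.** The plan states no SD, correlation, effect size or precision target, so there is no figure to reproduce.

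**Inputs from the protocol**
- Four arms, 1:1:1:1 (Sections 3.1 and 5.1.2), about 12 to 16 per arm (synopsis), so 48 to 64 in total.
- Fasted predose samples on Day 1 and on Days 15, 43 and 84 (Table 3.1).
- A single baseline value: "The baseline of biomarker data is defined as the last nonmissing assessment collected prior to the first dose of study medication".

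**Assumptions**
- Section 11.9 refers to Phase 1 variability but gives no figures.
- I take variance 1 per log measurement, correlation rb between baseline and each on-treatment visit, and correlation rp between on-treatment visits.

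**Step 1: variance of change from baseline**
- One visit: 2 − 2rb.
- Mean of three visits: (1 + 2rp)/3 + 1 − 2rb.
- If rb = rp = r, these are 2(1 − r) and (4/3)(1 − r). The ratio is 2/3 for any r.

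With rb = 0.5 the one-visit variance is 1, so the ratio equals (1 + 2rp)/3:

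| rp | Variance ratio | SE ratio | Interval narrower by | Equivalent sample |
|---|---|---|---|---|
| 0.5 | 0.667 | 0.816 | 18% | 1.50 × |
| 0.7 | 0.800 | 0.894 | 11% | 1.25 × |
| 0.8 | 0.867 | 0.931 | 7% | 1.15 × |
| 0.9 | 0.933 | 0.966 | 3% | 1.07 × |

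**Step 2: half-width for dose minus placebo**

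In units of the SD of a single-visit change, the half-width is t(2n − 2) × √(2/n) × SE ratio.
- n = 12: 0.85 for one visit, 0.69 averaged at rp = 0.5, and 0.85 × 0.931 = 0.79 at rp = 0.8.
- n = 16: 0.72 for one visit, 0.59 averaged at rp = 0.5, and 0.72 × 0.931 = 0.67 at rp = 0.8.

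**Step 3: baseline adjustment in both analyses**

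The variances become 1 − rb² and (1 + 2rp)/3 − rb². With rb = 0.5:
- One visit: 0.75.
- Averaged: 0.417, 0.550, 0.617 and 0.683 for rp = 0.5, 0.7, 0.8 and 0.9.
- SE ratios: 0.745, 0.856, 0.907 and 0.955, so the interval is 25%, 14%, 9% and 5% narrower.

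**Step 4: when averaging stops helping**

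Let the Day 15 effect be a fraction f of a plateau reached by Day 43. The averaged effect is (2 + f)/3 of plateau. For change scores, signal-to-noise improves on a single plateau visit only if (2 + f)/3 exceeds the SE ratio, that is f > 3 × SE ratio − 2:
- rp = 0.5: 3 × 0.8165 − 2 = 0.45.
- rp = 0.8: 3 × 0.9309 − 2 = 0.79.

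**Sensitivity**

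If correlation decays with time between visits (0.3 to 0.9 per 28 days), the SE ratio against Visit 5 alone is 0.62 to 0.70. With 30% to 50% measurement noise added it is 0.72 to 0.78. These structures leave out a higher correlation among on-treatment visits than with baseline, which is the case that shrinks the gain, so I do not rely on them.

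**The case against.** The best case for the plan is that it fits its own outcome. Section 2.1 describes the PD outcome as profiles from baseline through Day 98, and by-visit tables describe a profile. An average over Days 15 to 84 is a different target and presumes a near-stable effect from Day 15, which no section states. The study is descriptive and has no power target, so no stated criterion is missed. This stands. It is why the by-visit tables should stay and the Visit 5 estimate should sit beside the average. It does not supply a main estimate or an interval for dose versus placebo.

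A reader might infer three stronger criticisms that the documents do not support.
- *The plan never pools the visits.* The supplied text states no pooling, but a SAP is promised in Section 11.10, Section 3.2 foresees modeling, and some statistical content is not shown. Nor is dose choice said to rest on a single-visit contrast.
- *Each comparison rests on one value per participant.* Table 3.1 marks full collection at Visits 2 and 5 and sparse collection at Visits 3 and 4. Several intraday samples per visit are likely, although Table 3.2 is not visible. Every assessment is summarised, and restricting the main estimate to predose samples is a choice made here for comparability.
- *Participants who stop early vanish from the later rows.* Table 3.1 defines Visit 5 as Day 84 or the day of early discontinuation, and Sections 5.7.2 and 6.4 direct early stoppers to complete it. The actual issue is mixed exposure times within the Visit 5 row, which a combined analysis must also handle.

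**Conclusion.** The point holds as a cheap improvement to the stated analysis. It is not a flaw that invalidates the plan. On the protocol text, the primary dose-response analysis lacks a named main estimate per dose, an interval for the dose-versus-placebo difference, and an analysis combining the fasted predose samples at Visits 3 to 5.

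The precision to be gained is 18% of interval width for change from baseline if all correlations are equal. It falls to 11%, 7% or 3% if on-treatment visits correlate at 0.7, 0.8 or 0.9 against 0.5 with baseline. A reader might take 18% as the expected gain. The documents give no correlations, and if participants differ in their response to the drug the lower figures are more plausible.

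All of these figures assume equal variances on the log scale and a roughly stable effect from Day 15. If the Day 15 effect is under about 45% of plateau (equal correlation) or about 79% (on-treatment correlation 0.8), averaging lowers signal-to-noise.

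**What to change.** Add to Section 11.5.3 and the synopsis, and carry into the SAP:

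- For each of ALP, PPi and PLP, fit one repeated-measures model to the log ratio to baseline of the fasted predose samples at Visits 3, 4 and 5, with arm, visit, arm-by-visit and log baseline terms.
- Report each dose versus placebo with a 95% confidence interval in two forms: the equal-weight average over the three visits, and the Visit 5 estimate. Back-transform both to percentages.
- Assign an early-discontinuation Visit 5 by its actual study day and not as Day 84. Let the model handle missing visits, and state the missing-at-random assumption this makes.
- Keep the by-visit and postdose summaries as support.

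While editing, reconcile the list of markers that receive a 95% interval for percentage change: the synopsis names PPi and PLP, and Section 11.5.3 adds ALP.

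The cost is a few sentences of protocol and SAP text and one model per marker on data already scheduled, with no extra samples, visits or participants. The downside is that an average can blur a slow onset or drift. The adjacent Visit 5 estimate and the by-visit tables would show it.

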eCRF	electronic case report form			
CRO	contract research organization			
Ctrough	trough plasma concentration			
EC	Ethics Committee			
ECG	electrocardiogram			
EDC	electronic data capture			
EIU	exposure in utero			
ENPP1	ectonucleotide pyrophosphatase/phosphodiesterase 1			
EU	European Union			
CCI	CCI			
GCP	Good Clinical Practice			
CCI	CCI			
HPP	hypophosphatasia			
ICF	informed consent form			

ABBREVIATION	DEFINITION			
ICH	International Council for Harmonisation			
ICMJE	International Council of Medical Journal Editors			
CCI	CCI			
IRB	Institutional Review Board			
IRT	interactive response technology			
CCI	CCI			
LLN	lower limit of normal			
MedDRA	Medical Dictionary for Regulatory Activities			
Mg	magnesium			
MOA	mechanism of action			
CCI	CCI			
CCI	CCI			
PD	pharmacodynamic			
Pi	inorganic phosphate			
PK	pharmacokinetic			
PLP	pyridoxal 5'-phosphate			
PPi	inorganic pyrophosphate			
PXE	pseudoxanthoma elasticum			
SAE	serious adverse event			
SAP	statistical analysis plan			
SAVER	serious adverse event report			
CCI	CCI			
SoE	schedule of events			
SUSAR	suspected unexpected serious adverse reaction			
TBL	total bilirubin			
TEAE	treatment-emergent adverse event			
Tmax	time to reach maximum plasma concentration			
TMF	trial master file			
TNAP	tissue-nonspecific alkaline phosphatase			
ULN	upper limit of normal			
CCI	CCI			
VEGF	vascular endothelial growth factor			

